#### Restorative procedure

All restorations (25 for each restorative material) were performed by the same operator to ensure consistency ([name]). Twenty-five patients received a total of 75 restorations. As such, each patient received three Class II restorations randomly: one with Sonic Fill (Kerr); a conventional viscosity composite, Filtek Z-250 (3M ESPE);

and the other with x-tra fil (VOCO), a high-viscosity bulk-fill composite. Local anesthesia was applied for patients who complained of pain or sensitivity. The cavity preparation was made by using a spherical diamond bur (Meisinger Dental Burs, Hager and Meisinger GmbH, Neuss, Germany) on a high-speed air turbine. Infected dentin in the cavity was removed by carbide round burs used with a low-speed handpiece, and no bevel was prepared. Discolored but hard dentine was left in place at the cavity floor. The cavities were designed according to the principles of minimally invasive dentistry. None of the cavity preparations involved one or more cusps. All of the gingival margins included sound enamel. The operative field was cleaned with an air/water spray, gently air-dried, and then carefully isolated with cotton rolls and suction. The outline shape of the preparations was limited to the removal of caries; as such, no additional retention and bevel was prepared. For each restoration, the tooth type (molar/premolar) and cavity type (number of restored surfaces) were recorded. All patients received oral hygiene instructions and a professional tooth cleaning before initiating the restorative intervention. No liner or base was used.

An ivory type matrix system (Hahnenkratt, Königsbach-Stein, Germany) and wooden wedges were used. To remove water, the cavities were rinsed for 10 s and air-dried for 5 s. Three adhesive systems were used: OptiBond™ XTR (Kerr), Solobond M (VOCO), Adper Single Bond 2 (3M ESPE). The adhesives were applied following the manufacturer's instructions (**Table 1**). All light-curing procedures were performed with the same LED-curing unit (Model BUILT-IN C, Guilin Woodpecker Medical Instrument Co., Ltd., Guilin, Guangxi, China) operating in a continuous mode while emitting a light-intensity of 1200 mW/cm^2 according to the manufacturers' recommended polymerization times. The light was directed perpendicular to the occlusal surface.

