Three different restorative resins were placed in each patient, resulting in a total of 75 restorations; 25 of the preparations were restored using the bulk-fill resin composite Sonic Fill (Kerr, Orange, CA, USA) (n = 25), 25 of them were restored with Filtek Z-250 (3M ESPE, St Paul, MN, USA) (n = 25), and 25 of them were restored with x-tra fil (VOCO, Cuxhaven, Germany), according to the manufacturers' instructions (**Table 1**). The Filtek Z-250 restorative material was applied using an incremental filling technique, beginning at the gingival wall. The increments, not exceeding 2 mm in thickness, were added to complete the proper anatomical form. Each increment was polymerized for 20 seconds. The x-tra fil restorative material was placed in bulk up to 4 mm in thickness and cured for 10 seconds with the same curing unit. The other bulk-fill resin composite material, Sonic Fill, was applied to the bonded cavities with sonication (SonicFill Handpiece, Kerr) and photo-polymerized for 40 s according to the manufacturer's instructions. The randomization of restorative material was done using a table of random numbers.

After removal of the matrix system, the restorations on the teeth in all groups were light-cured for a further 20 s from the buccal, lingual, and occlusal aspects. The cotton rolls were then removed, and occlusion and articulation were checked and adjusted. The surface of the teeth was finished with fine-grit diamond instruments (Diatech, Coltene, Switzerland), polishing disks (Sof-Lex, 3M-ESPE, MN, USA), and rubber polishing instruments (One Gloss, Shofu, Kyoto, Japan). Water-cooling was used throughout the finishing procedures. We used abrasive strips (3M ESPE, St. Paul, MN, USA) on the proximal surfaces when necessary. We checked the quality of the interproximal contact and the cervical adaptation by means of dental flossing and bitewing radiographs. The clinical procedure of tooth preparation and placement of restorations was performed by the same operator.

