### **Periods and evaluation criteria**

One week after restoration placement (baseline), patients were recalled and restorations were examined clinically. Direct clinical evaluation of restorations was performed using the USPHS criteria (**Table 2**) by two independent investigators ([name] and [name]) using mirrors, probes, and bitewing radiographs and scored as Alpha, Bravo, or Charlie. Alpha corresponded to excellent, Bravo to clinically acceptable, and Charlie to clinically unacceptable results (**Table 2**). Patients were recalled at 6, 12, and 24 months for assessments of the restorations, using the same criteria as at baseline. At each recall, the same two calibrated evaluators, who were blinded to the restoratives used for cavities and patients, examined the restorations. To ensure a double-blind study, the evaluators were not informed about which filling material had been used on which teeth. When disagreement occurred during the evaluation, the final decision was made by the consensus of both examiners. All evaluations were carried out under a dental operating light, using flat-surfaced mouth mirrors and dental explorers. Postoperative sensitivity was assessed by blowing a stream of compressed air for three seconds at a distance of 2 to 3 cm from the restoration under isolation from the adjacent teeth with gauze and by moving the probe over the restored tooth surface.

The statistical analyses were carried out with the IBM SPSS version 22.0 software package (SPSS, Chicago, IL, USA). The restoration groups for each category were compared using the Pearson chi-square test, and the Cochran Q-test was used to compare the changes across different time points within each restorative material ( $p < 0.05$ ).

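### The between-material comparison yields only an unpaired chi-square p-value, which with 25 restorations per material cannot show how different the materials might be and cannot be computed when all grades coincide

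*Combined protocol and SAP*

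**What the plan says.** The whole analysis plan is the last paragraph of *Periods and evaluation criteria* in the combined protocol and SAP. Between materials, "The restoration groups for each category were compared using the Pearson chi-square test". Within each material, change over the visits is tested with Cochran's Q. The threshold is p < 0.05. The paragraph names no effect estimate, confidence interval, equivalence or non-inferiority margin, or rule for a criterion on which nothing varies.

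The same section says that restorations are "scored as Alpha, Bravo, or Charlie" and gives the grades their meaning: "Alpha corresponded to excellent, Bravo to clinically acceptable, and Charlie to clinically unacceptable results". Assessments are at baseline (one week) and at 6, 12 and 24 months.

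*Restorative procedure* fixes the size and structure: "Twenty-five patients received a total of 75 restorations" and "Three different restorative resins were placed in each patient, resulting in a total of 75 restorations". Each material therefore has 25 restorations, one per patient, and the comparison between materials is matched within patients.

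**The concern.** A p-value at a fixed threshold answers one question: whether the data are surprising if the materials do not differ. With 25 matched sets, a p-value above 0.05 is expected both when the materials perform alike and when they differ by a clinically relevant amount that the study is too small to show. The plan provides nothing that separates these two situations.

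The gap is widest for the worst grade. If no Charlie occurs, a Charlie-versus-not comparison has an empty column and no test result. The same happens on any criterion where every restoration has the same grade. What is left is a count of 0 of 25 per material with no statement of precision. How far apart the unacceptable rates could still be would then go unanswered.

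**Working it through.** **Inputs from the documents.** 25 patients, three restorations each, one per material (*Restorative procedure*); three grades per criterion, four assessments, Pearson chi-square, Cochran's Q and p < 0.05 (*Periods and evaluation criteria*). The only figure to reproduce is the total: 25 x 3 = 75, which agrees. Sidedness is not stated; two-sided 95% limits are assumed below.

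**1. A non-significant result with few events.** Take two materials where 3 patients have a non-Alpha grade with material A only, 1 with material B only, and none with both (illustrative counts).
- Exact McNemar: 2 x [C(4,0) + C(4,1)]/2^4 = 2 x 5/16 = 0.625.
- Pearson chi-square on 3/25 versus 1/25: 50 x (3 x 24 - 1 x 22)^2/(25 x 25 x 4 x 46) = 125,000/115,000 = 1.09, p = 0.30.
- Estimated paired difference: (3 - 1)/25 = 8 points.
- Tango score limits solve (b - c - n*d)/sqrt{n[2q + d(1 - d)]} = ±1.96, with b = 3, c = 1, n = 25 and q the constrained estimate of the B-only probability. At d = -0.102, q = 0.164 and the ratio is +1.96. At d = 0.271, q = 0.020 and the ratio is -1.96. The interval is -10.2 to +27.1 points.

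Both tests give p > 0.05, and the interval shows how little that excludes.

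**2. When the planned tests have no value.**
- Chi-square: with 0/25 in each of three materials, the expected count in the event column is 25 x 0/75 = 0. Each term (O - E)^2/E is 0/0, and the software rejects the table.
- Cochran's Q = (k - 1)[k*sum(C_j^2) - T^2]/[k*T - sum(R_i^2)], with k = 4 visits, C_j the visit totals, R_i the totals per restoration and T the grand total. If no restoration changes score, each R_i is 0 or 4. Then sum(R_i^2) = 4T and the denominator is 0. Running it on constant 25 x 4 data returned no number.
- Counter-check: with no Charlie but a mix of Alpha and Bravo, for example 22/3, 19/6 and 20/5, the chi-square is 1.23 on 2 degrees of freedom, p = 0.54. It is defined, but it carries no information about Charlie.

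**3. How often no Charlie would be seen.** The documents give no Charlie rate, so a range is assumed, treating the 75 restorations as independent although they are grouped three to a patient.

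| Assumed rate | Chance of none in 75 |
|---|---|
| 1% | 0.99^75 = 47% |
| 2% | 0.98^75 = 22% |
| 3% | 0.97^75 = 10% |
| 5% | 0.95^75 = 2% |

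**4. What 0/25 leaves open.**
- One material, exact upper 95% limit: 1 - 0.025^(1/25) = 13.7%.
- Two materials, Tango with no discordant pairs: d = z^2/(n + z^2) = 3.84/28.84 = 13.3 points in either direction. Miettinen-Nurminen gives 13.6 and Agresti-Caffo 10.1, both for unpaired groups.
- With assumed dropout: 3.84/25.84 = 14.9 points at n = 22, and 3.84/23.84 = 16.1 at n = 20.
- With Bonferroni adjustment for three pairs (z = 2.394): 5.73/30.73 = 18.6 points at n = 25.
- A material with a true rate of 5% or 10% would show 0/25 with probability 0.95^25 = 28% or 0.90^25 = 7%.

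**The case against.** The strongest reply concerns scope. The plan uses a three-grade scale and never defines a Charlie-versus-not outcome. A reader might infer that both tests fail on every criterion without a failure. That is not so: a mix of Alpha and Bravo keeps the chi-square defined, and Cochran's Q on Alpha versus not-Alpha is defined once any restoration changes score. This part of the reply stands, and the point is limited accordingly.

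A reader might also infer that an absence of Charlie is likely. The documents do not support that. They give no rate, and even at an assumed 1% the chance is just under one half; it falls to about 2% at 5%. It is a possibility to plan for.

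A third tempting inference is that the trial intends to declare the materials equal. Nothing in the text says so: it reports no results, gives no rule for reading p > 0.05, names no primary endpoint and makes no equivalence claim. A test that cannot be computed does no harm by itself, and a reader shown 0/25 could work out the 13.7% limit unaided. Nor does silence about intervals mean that none would be reported.

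What remains is that the plan commits to no measure of difference or precision, and that its between-material test ignores the within-patient matching. Leaving readers to derive a single-material limit does not give them the paired difference, because that needs the patient-level cross-classification.

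**Conclusion.** The point holds as an analysis that should be improved. A p-value-only, unpaired comparison with 25 per material cannot say how different the materials could be. In the worked example, p = 0.63 goes with an interval from -10 to +27 points. At 0/25 in both materials, a difference of about 13 points in either direction remains compatible with the data.

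The 13-point figure assumes two-sided 95% limits, all 25 patients evaluable at 24 months, the Tango method and one unadjusted comparison. Dropout or adjustment for three pairs widens it to roughly 15 to 19 points in the cases computed. Failure of the chi-square is confined to criteria where all restorations share one grade and to a Charlie-versus-not table with no Charlie; failure of Cochran's Q is confined to materials where no score changes over the visits. The data remain usable, so this is a weakness in what the plan produces from them.

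**What to change.** For each criterion at 24 months, report:
- each material's proportion non-Alpha and proportion Charlie, with exact 95% limits;
- each of the three pairwise within-patient differences, with a 95% paired score (Tango) interval, including when counts are zero, labelled either as unadjusted or as adjusted for the three comparisons;
- the number of patients evaluable for each pair.

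State that no test is computed when nothing varies, that the conclusion rests on the interval, and that neither p > 0.05 nor an uncomputable test will be described as similarity or absence of difference.

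This needs a few lines of analysis text and one more table, from data the study already collects. No patients, visits or clinical procedures change. The downside is that the conclusion will be less favourable than a bare count of no failures or a non-significant p-value would suggest. Tango is one reasonable choice among several, so the method should be named in advance.

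### Cochran's Q needs a yes/no response, but the score has three levels and no cut-point is stated; where all three levels occur, the choice of split can decide significance.

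*Combined protocol and SAP*

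**What the plan says.** The section *Periods and evaluation criteria* sets the outcome scale: "Direct clinical evaluation of restorations was performed using the USPHS criteria", with each restoration "scored as Alpha, Bravo, or Charlie". The levels are ordered: "Alpha corresponded to excellent, Bravo to clinically acceptable, and Charlie to clinically unacceptable results".

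There are four assessments. The first comes one week after placement: "One week after restoration placement (baseline), patients were recalled and restorations were examined clinically". Then: "Patients were recalled at 6, 12, and 24 months for assessments of the restorations, using the same criteria as at baseline".

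The statistical paragraph at the end of that section names two tests. Between materials: "The restoration groups for each category were compared using the Pearson chi-square test". Over time: "the Cochran Q-test was used to compare the changes across different time points within each restorative material", at the 0.05 level. It does not say how three levels become two for the second test. Table 2 is cited in the section for the criteria and the meaning of the scores; its content is not in the available text.

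On the design, *Restorative procedure* says: "Three different restorative resins were placed in each patient", with 25 restorations per material.

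**The concern.** Cochran's Q is defined for a binary response measured repeatedly on the same unit. A three-level score has to be collapsed first, and the level definitions offer two natural boundaries: excellent against the rest, or unacceptable against the rest. The plan assigns neither to the test.

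Neither boundary registers both steps of deterioration. Alpha versus the rest does not see a restoration go from Bravo to Charlie, which is the step from acceptable to unacceptable. Charlie versus the rest does not see Alpha to Bravo.

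With no stated split, it could be chosen after the scores are seen, and a reader could not tell whether a reported change means loss of excellence or clinical failure.

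A separate point concerns the comparison of materials. Q is run within each material, so its p-values do not compare materials. The only between-material test named treats the three groups as independent, although every patient carries all three.

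**Working it through.** The plan gives no power or effect calculation for this analysis, so there is no figure to reproduce.

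**Inputs from the document:** 25 restorations per material (25 patients × 3 materials = 75); k = 4 visits; three ordered levels; significance level 0.05.

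**Assumed:** all score patterns, written below in the order baseline, 6, 12, 24 months, with every visit present unless stated.

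**Formulas.**
- Cochran: Q = (k−1)(kΣC² − N²)/(kN − ΣL²), where C is the count of ones per visit, L the count per restoration and N the total.
- Friedman, corrected for ties: F = (k−1)ΣD²/Σd², where d is each within-restoration rank minus 2.5 and D is the sum of d at a visit.
- Both are referred to chi-square on 3 df. Exact p-values use the full within-restoration permutation distribution.

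**Example 1: 4 go A,A,A,B; 2 go A,B,B,C; 19 stay Alpha.**
- Alpha versus rest: C = 0, 2, 2, 6; N = 10; ΣC² = 44; ΣL² = 4×1 + 2×9 = 22. Q = 3(176 − 100)/(40 − 22) = 228/18 = 12.67.
- Charlie versus rest: C = 0, 0, 0, 2; N = 2. Q = 3(16 − 4)/(8 − 2) = 6.0.
- Friedman: D = −5, −2, −2, 9; ΣD² = 114; Σd² = 4×3 + 2×4.5 = 21. F = 3×114/21 = 16.29.

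**Example 2: 1 goes A,A,A,B; 4 go B,B,B,C; 20 stay Alpha.** This needs four Bravo scores at baseline.
- Alpha versus rest: C = 4, 4, 4, 5; N = 17; ΣC² = 73; ΣL² = 4×16 + 1 = 65. Q = 3(292 − 289)/(68 − 65) = 3.0.
- Charlie versus rest: C = 0, 0, 0, 4; N = 4. Q = 3(64 − 16)/(16 − 4) = 12.0.
- Friedman: D = −2.5, −2.5, −2.5, 7.5; ΣD² = 75; Σd² = 15. F = 15.0.

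| Example | Analysis | Statistic | p (chi-square) | p (exact) |
|---|---|---|---|---|
| 1 | Q, Alpha vs rest | 12.67 | 0.0054 | 0.0029 |
| 1 | Q, Charlie vs rest | 6.0 | 0.11 | 0.25 |
| 1 | Friedman | 16.29 | 0.0010 | 0.0003 |
| 2 | Q, Alpha vs rest | 3.0 | 0.39 | 1.0 |
| 2 | Q, Charlie vs rest | 12.0 | 0.0074 | 0.016 |
| 2 | Friedman | 15.0 | 0.0018 | 0.0039 |

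**Range.** Start with all 25 Alpha. Let 0 to 8 go A,A,A,B and 1 to 5 go A,B,B,C, which gives 9 × 5 = 45 combinations. The two splits fall on opposite sides of 0.05 in 13 (21 by exact p), all with only 1–2 Charlie (1–3 by exact p). In the other 32 (24 by exact p) the split does not change the verdict.

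**Two-level check.** With 4 A,A,A,B, 2 A,B,B,B and 19 Alpha, Q and Friedman are both 12.67. When only two levels occur, there is no problem.

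**Small counts.** When Charlie is first seen at 24 months in c restorations, Q = 3c. For c = 1, 2, 3 the chi-square p is 0.39, 0.11 and 0.029; the exact p is 1.0, 0.25 and 0.0625. At c = 3 the approximation and the exact test disagree at 0.05.

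**Missed visits.** Both tests need complete rows. If one A,B,B,C restoration in Example 1 misses any visit, the Charlie split falls to Q = 3.0, p = 0.39. If both do, no Charlie remains in the test.

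**The case against.** The strongest reply is that the problem is conditional. It needs all three levels on one criterion within one group of 25, and the documents give no scores to show that this happened. Example 2 assumes four Bravo scores one week after placement, which nothing in the text supports. The 45 combinations are an unweighted grid over chosen ranges, not a frequency. All of this stands: the examples show what is possible, not what is likely.

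Table 2 might show criteria with only two levels, or a grouping. That cannot be excluded. It is cited only for the criteria and score meanings, and the statistical paragraph does not refer to it.

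The two splits also ask different questions (any deterioration, or failure), so different p-values are expected, and naming a cut-point might be enough. On the grid above, Friedman and the Alpha split agree at 0.05 in 43 of 45 combinations by chi-square p. But every combination there starts from Alpha. In Example 2 the Alpha split gives p = 0.39 while four restorations become unacceptable, and Friedman gives p = 0.0018. Naming that split would not recover the lost step.

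Finally, the flaw affects time trends within a material, not the comparison of materials, and missed visits are not reported in the text. Both are correct. They limit the reach of the point without removing it.

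**Conclusion.** The concern holds and should be fixed. Where all three levels occur, the named test cannot be run on the score as recorded, the available text states no split, and either split loses one step of deterioration. With 25 restorations and few reaching Charlie, the split can move the p-value across 0.05 in either direction: 0.0054 against 0.11 in one assumed pattern, 0.39 against 0.0074 in another. Where only two levels occur, Q is sound.

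This rests on assumed scores, on Table 2 containing no cut-point, and, except in the missed-visit case, on complete data. How often the condition arises is unknown. The dependence between materials that the Pearson chi-square ignores is a separate fault and holds independently of these assumptions.

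**What to change.** 1. Test change over time within each material on the three-level score, using Friedman's test (restoration as block, four visits) or an ordinal repeated-measures model.
2. Report Charlie yes/no separately, with counts and denominators at each visit and Cochran's Q at that stated cut-point. Friedman alone does not identify failure: its statistic is 15.0 both when 5 of 25 go A,B,B,B and when 5 of 25 go A,B,B,C, although Charlie counts at 24 months are 0 and 5.
3. Use exact p-values where few restorations change.
4. State how many restorations are dropped from Friedman and Q for a missed visit, and keep their available scores in the visit counts.
5. As a separate change, compare the three materials within patient at 24 months (Friedman, patient as block), and do not infer differences between materials from separate within-material p-values.

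The cost is revised analysis wording and a few extra analyses of existing scores. No new data or visits are needed.
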